11 JANUARY 2024

Wave Neuroscience, Inc., Newport Beach, California United States

PROTOCOL eTMS-PTSD-001

Electroencephalogram (EEG) personalized Transcranial Magnetic Stimulation (eTMS)

for Post-Traumatic Stress Disorder

(eTMS for PTSD)

STUDY SYNOPSIS

Study Objective	Evaluate the safety and efficacy of electroencephalogram (EEG) personalized transcranial magnetic stimulation (eTMS) for the treatment of Post-Traumatic Stress Disorder (PTSD).
Study Design	 Stage 1: Open-label Safety Pilot Study Stage 2: Randomized, double-blind, sham-controlled trial of eTMS, with open label period following sham control.
Study Population	 Veterans and First Responders with PTSD male or female 22 - 65 years of age any racial/ethnic background who meet the eligibility criteria
Research Group	Principal Investigator: [name] Head of Research Wave Neuroscience, Inc. [name] [contact] [contact] Study Chair: [name], PhD, JD Visiting Faculty Department of Neurobiology and Behavior [name] [contact] [contact] ; [contact]

Data Center:
Maven LLC
[name]
[name]
Point of contact
[name]
[contact]
Clinical site#1:
Wright State University
Center of Neuroimaging and Neuro-Evaluation of Cognitive
Technologies
[name]
[name]
Site Principal Investigator:
[name], MBA
Director, Research Associate Professor
[contact]
[contact]
Additional Clinical sites:
Up to 3 additional Clinical Sites may be added in Stage 2 to increase
enrollment and geographic diversity.
Supportive Treatment Center
JLC Services
[name]
[name]
Point of Contact:
[name]
[contact]
[contact]
FDA IDE Sponsor:
Wave Neuroscience, Inc.
[name]
[name]
President:
[name], DO
[contact]
*This study was commissioned by the State of Ohio (2021 RFP Number
SRC000002472, Index Number DMH009) to address the ongoing crisis among
Veteran population in the areas of mental health and substance use. The goal for this work is to develop therapies that work for the complex Veteran patient for
whom there are currently no good therapeutic options.

	Inclusion Criteria
Eligibility	Participants must meet all inclusion criteria to qualify for enrollment in
Criteria	the study:
	1. Willing and able to consent to participate in the study via signed
	Informed Consent
	2. Age $22 - 65$ years

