All subjects who finish BL assessments and meet inclusion/exclusion criteria will be randomized into one of two groups, "Active eTMS" and "Sham eTMS", in a 1:1 ratio, stratified by clinic. Stage 2 will consist of a randomized period and an open-label period. During the randomized period, the Active eTMS group will receive Active eTMS and the Sham eTMS group will receive Sham eTMS twice per day, with 20 total treatments delivered in a 2 or 3-week period. Following the randomized period of the study, all Sham eTMS subjects will have the option of participating in the open-label portion of the study. Those who choose to participate in open-label treatment will receive 20 Active eTMS sessions, twice per day, which must be completed in a period of 21 calendar days.

All groups will undergo an assessment of symptoms at baseline, before Week 6 (F1), and then again at the end of Week 10 (F2). The primary efficacy endpoint, and outcome time point, is Wave Neuroscience, Inc. Protocol eTMS-PTSD Rev 1.1 11 January 2024 PAGE 28 change in Post-Traumatic Stress Disorder symptoms between the Baseline (BL) and the first follow-up (F1). The primary efficacy outcome will be measured using the PCL-5. Safety outcomes will be measured by recording adverse events, incidence and type.

PARTICIPANT POPULATION

The enrollment goal for the combined two stages of the study is 170 participants of any gender or ethnic background, age 22-65 years, with Post-Traumatic Stress Disorder. Thirty (30) participants will be part of Stage 1 and be provided with open-label treatment to evaluate safety of eTMS in this population. 140 participants will be part of Stage 2, randomized to either active or sham eTMS, in a 1:1 allocation ratio, stratified by recruitment site. Participants randomized to sham eTMS in Stage 2 will receive an additional series of open-label active eTMS following the randomized portion of Stage 2.

Inclusion Criteria

Participants must meet all following inclusion criteria to qualify for enrollment into the study:

- 1. Willing and able to consent to participate in the study via signed Informed Consent
- 2. Age 22 65 years
- 3. Provisional diagnosis of PTSD according to Veterans Administration PCL-5 rubric fulfillment AND cutpoint score of 31 or above
- 4. Positive identification as either a Veteran, or First Responder (e.g., emergency medical service provider, firefighter, or any other emergency response personnel)

Exclusion Criteria

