If a potential participant is a female of child-bearing potential (i.e., not 2 years post-menopausal, and not sterile by tubal ligation or hysterectomy), a urine pregnancy test will be conducted. Unless the test is negative, the individual is not eligible to participate. The site Investigator or Clinic Coordinator will provide the result of the test to the potential participant. If the result is positive or indeterminate, the individual will be advised to confirm with a health care provider. A copy of the test package insert will be provided to each individual and the possibility of both false negative and false positive results noted. If it is determined at a later date, after the screening period has expired, that the potential participant is not pregnant, then the screening process can be repeated in totality, and if she is eligible, she may be enrolled.

Eligibility is not confirmed until an eligibility checklist and any supporting materials needed have been reviewed by the site Investigator, and s/he has confirmed, in writing that enrollment may proceed. No participant will be enrolled without such written confirmation.

Continued eligibility related to safety factors will be checked before conducting active eTMS treatment in the open-label extension for those participants who opt-in.

Additional Considerations for Stage 2 Randomized Controlled Trial

Randomization

Participants in Stage 2 will be assigned randomly to one of the two treatment groups (Active eTMS treatment vs Sham eTMS treatment). The treatment allocation will be in a 1:1 ratio, using permuted variable blocks of size 2, 4, and 6.

Participants will be randomized at the beginning of the first treatment visit. This will occur after giving informed consent at SC; after eligibility is determined from data collected at the BL Visit; after all data necessary to determine eligibility is reviewed and documented on the Eligibility data collection form; and **after written confirmation to proceed is provided by the site Investigator**. Participants will be randomized at the last possible moment (just prior to the first treatment) in order to avoid randomizing an eligible potential participant who thereafter changes his or her mind about participation before the first study treatment can be delivered, or who is not well enough to be treated on that occasion.

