The study intends to use a commercial randomization system that supports interactive web response that is capable of supporting blinded studies and providing stratification according to the eTMS-PTSD-001 randomized study design. If multiple sites are used in the Stage 2 RCT, the randomization schema will be stratified by site.

Unblinding

The randomization assignment information will be kept in a separate file by the PI. It will not be accessible to the study investigators before the study is completed or terminated unless unblinding is needed for an individual participant for safety reasons. The site Investigator may request unblinding for safety reasons The study will be organized so that unblinding for safety purposes may be done at any time should an emergency arise. In most cases, the unblinding will be part of managing a SAE, and will be reported with the SAE to the IRB. The unblinded participant will be withdrawn from the randomized treatment protocol. In all cases, any breaking of the blind must be followed by a written narrative of the event within 5 days. Every attempt will be made to collect full follow-up data from participants withdrawn from the treatment protocol.

The study leadership will convene a for-cause DSMB meeting to review adverse events leading to unblinding that require immediate and real-time attention by that body. The Study Chair and Principal Investigator will have full access to the unblinded subject specific adverse event reports.

Prior and Concomitant Medications/Neuromodulation Treatments

All prior and concomitant medications, and neuromodulation treatments must be listed in the participant's study record and recorded in the study database. Participants will be questioned at F1 and before each treatment visit in Stage 1 and Stage 2, including the open-label period concerning any new or changed medications or neuromodulation treatments.

For each medication taken, a minimum of the following information will be collected:

- Medication name
- Indication for which the medication was given
- Dose, route, and frequency of administration
- Date started
- Date stopped

Participants should stay on their usual medication regimens at stable doses during the entire course of the trial. This includes OTC medications. Questions regarding the use of concomitant medications should be addressed to the medically qualified Investigator who will consult with the Study PI and Study Chair regarding any methodological implications.

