
Stage 2

Stage 2 of the trial is intended to investigate efficacy and safety of the procedure in the target population. The primary efficacy outcome is a measure of PTSD symptom severity. PTSD symptom reduction will be calculated as the arithmetic reduction in PCL-5 scores between BL and F1. See the above Data Collection section for a description of this assessment.

Safety will be characterized by adverse event incidence, relatedness, severity, type, subsequent treatment/intervention required, and resolution status.

SAMPLE SIZE CONSIDERATIONS FOR STAGE 1

A convenience sample size of thirty (30) will be treated in the safety pilot stage in order to detect common adverse effects or safety concerns.

SAMPLE SIZE CONSIDERATIONS FOR STAGE 2

Sample size assumptions:

[figure not shown]
- Design variable is change in PCL-5 between BL and F1.
 - Mean in first responders = 38.73 (SD = 18.68) (Morrison, Su, Keck, & Beidel, 2021)
 - Primary outcome clinically important difference = 15(10-20) (U.S. Department of Veterans Affairs, 2022)
- Planned estimated effect size +0.8 SD_{difference}, for a difference in Active eTMS versus Sham eTMS group mean pre-post PCL-5 scores = 15, with pooled SD_{difference} = 18.68
- Assignment ratio =1:1 for Active eTMS vs. Sham eTMS
- 10% loss to followup

- Type 1 error = 0.05 (2-sided)
- Statistical power = .985
- Method of calculation Sample size and power for given detectable difference between two mean difference scores using Student's t-test according to method of Dupont & Plummer

Sample size requirements:

- Total completers: 108 (90% 54 per group) See Figure 2 below
- Total to be randomized:120 (60 per group)

FIGURE 2: Primary efficacy outcome, PCL-5. Statistical power by number of completers per treatment group for Type 1 error 0.05 (.985) and 0.01 (.938)

DATA AND SAFETY MONITORING BOARD

A Data and Safety Monitoring Board (DSMB) comprised of at least 3 **independent** subject matter, medical, clinical trial methods, and biostatistics experts will be constituted to review the protocol, recruitment progress, site performance, study conduct, and safety data. The Board will request analyses, and will make recommendations regarding study continuation, amendment, or termination, as well as the advisability of adding up to 3 additional research sites.

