The primary efficacy outcome analysis will be conducted on the ITT population. The primary efficacy outcome measure is arithmetic change in PCL-5 score between BL and F1. The primary efficacy hypothesis is the superiority of eTMS treatment over sham eTMS treatment in participants with PTSD. Missing values will be imputed. The analysis of the primary outcome will be a linear regression of the change in PCL-5 total score between BL and F1, with independent variables being the BL PCL-5 total score and a dummy variable for the two treatment groups.

Missing F1 PCL-5 total scores will be addressed using multiple imputation. Missing PCL-5 total scores will be estimated (i.e., imputed) from a linear regression model to be determined from observations in which the F1 PCL-5 score is not missing; covariates considered for inclusion in the model will be the BL PCL-5 total score, a dummy variable for treatment group, and other potentially associated variables (e.g., age, gender, PTSD severity, military status, and number of treatments. The linear regression model will be chosen using the LASSO method with cross-validation, implemented in SAS PROC GLMSELECT. The set of variables to be considered for inclusion will be determined before the imputation is performed. After the form of the linear regression model is determined, at least 20 data sets will be created with the missing F1 PCL-5 values imputed, using the linear regression analysis (linear regression of change in PCL-5 score on BL score and a dummy variable for treatment group)

will be performed for each of the imputation datasets. SAS PROC MIANALYZE will then be used to combine the regression results from the previous step and form the final MI analysis results. Since there will be multiple imputed values for each missing F1 PCL-5 score, the analysis will account for variability in the missing values. This process assumes that missing values are missing at random (MAR), i.e., they may depend on values of other variables measured at the same time, but not on the non-missing values. The following sensitivity analyses will be conducted for missing PCL-5 total scores at F1: 1) analysis of non-missing F1 PCL-5 total scores; 2) analysis in which missing F1 PCL-5 total scores will be replaced with the best PCL-5 total score possible; and 3) analysis in which missing F1 PCL-5 total scores will be replaced with the worst PCL-5 total score possible.

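### Stage 2 randomisation is stratified by site, but the primary regression leaves site out; if several sites enrol, adding it recovers precision at almost no cost

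*Combined protocol and SAP*

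**What the plan says.** **Randomisation.** The Stage 2 design section allocates participants "in a 1:1 ratio, stratified by clinic". The Randomization section makes the stratification conditional: "If multiple sites are used in the Stage 2 RCT, the randomization schema will be stratified by site". Allocation is 1:1 "using permuted variable blocks of size 2, 4, and 6".

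**Number of sites.** One clinical site is named. The synopsis adds: "Up to 3 additional Clinical Sites may be added in Stage 2 to increase" enrolment and geographic diversity. The Data and Safety Monitoring Board section asks the board to advise on study conduct "as well as the advisability of adding up to 3 additional research sites". Stage 2 could therefore have one to four sites.

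**Primary model.** Under Primary outcome efficacy analysis, change in PCL-5 from baseline to F1 is regressed "with independent variables being the BL PCL-5 total score and a dummy variable for the two treatment groups". The same two-term model is restated for each imputed data set: "linear regression of change in PCL-5 score on BL score and a dummy variable for treatment group".

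**Imputation.** The candidate covariates are given as examples and site is not among them. Then: "The linear regression model will be chosen using the LASSO method with cross-validation".

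**Site in the analysis.** The paragraph on poolability, at the end of the same section, explores the site main effect and the site-by-treatment interaction in a separate analysis. Nothing there feeds back into the primary test.

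**The concern.** Small blocks within site keep the arms nearly balanced at every site, so most between-site variation cancels from the treatment contrast. A model without site does not know this. It leaves the between-site variation in the residual, and the reported standard error is larger than the true sampling variability of the estimate.

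The p-value and confidence interval are then conservative: some of the precision that stratification provides is not used. This matters most if the true effect is near the lower end of the 10 to 20 point range that the sample size section gives as clinically important. There, power is about 80% rather than 98.5%.

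**Working it through.** **Inputs from Sample Size Considerations for Stage 2 and the DSMB section:** 54 completers per arm, difference 15 points (clinically important range 10 to 20), SD 18.68, design alpha 0.05 two-sided, final-analysis alpha 0.049 two-sided.

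**The plan's own figure.** Standard error = 18.68 × √(2/54) = 3.595, and 15/3.595 = 4.17. A noncentral t with 106 df at alpha 0.05 gives power 0.9852, matching the stated 0.985.

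**Assumption.** Let r be the share of residual variance in PCL-5 change due to site. The documents give no value, so a range is shown. Arms are taken as balanced within site, and the total SD stays at 18.68.

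**Formulas** (normal approximation, z = 1.969 for alpha 0.049):
- SE reported without site: 3.595
- SE of the design: 3.595 × √(1 − r)
- Overstatement: 1/√(1 − r) − 1
- Actual type I error without site: 2 × [1 − Φ(1.969/√(1 − r))]
- Power without site: 1 − Φ[(1.969 × SE reported − δ)/SE design]
- Power with site: 1 − Φ(1.969 − δ/SE design)

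| | r = 2% | r = 5% | r = 10% |
|---|---|---|---|
| SE of the design | 3.56 | 3.50 | 3.41 |
| Overstatement of SE | 1.0% | 2.6% | 5.4% |
| CI half-width with site (7.08 without) | 7.01 | 6.90 | 6.71 |
| Actual type I error at nominal 0.049 | 0.047 | 0.043 | 0.038 |
| Power at 15 points, without → with | 0.987 → 0.988 | 0.988 → 0.990 | 0.990 → 0.992 |
| Power at 10 points, without → with | 0.794 → 0.800 | 0.798 → 0.812 | 0.804 → 0.832 |

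The site-adjusted model reaches the unadjusted model's power with a smaller sample: 2.4% (r = 5%) to 4.8% (r = 10%) smaller at 15 points, and 3.6% to 7.1% smaller at 10 points.

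**Larger sample.** The Study Design section gives 140 randomised and 126 completers, against 120 and 108 in the sample size section; these need reconciling separately. With 63 per arm, the 10-point gains are 0.856 to 0.867 (5%) and 0.863 to 0.885 (10%). At 15 points they are 0.1 of a percentage point or less. The overstatement and the actual type I error depend on r, not on sample size.

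**Simulation of the null.** 108 completers, blocks of 2, 4 and 6 within site, t-tests, 20,000 trials per case, for two equal sites, four equal sites and four unequal sites. Type I error without site was 0.043 to 0.046 at r = 5% and 0.035 to 0.042 at r = 10%. With site, over all values of r tried (0 to 20%), it was 0.045 to 0.052. With four equal sites and r = 10%, the mean reported SE was 3.61 against an actual SD of the estimate of 3.42.

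**Simulation of power.** Four sites of 27, 12,000 trials per case. At 10 points, power rose from 0.787 to 0.801 (5%) and from 0.785 to 0.817 (10%). At 15 points it rose from 0.984 to 0.987 and from 0.987 to 0.990. Estimates were unbiased (means 10.01 and 9.98 when the truth was 10).

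**Cost if site has no effect.** Noncentral t at 10 points, four sites: 105 df without site and 102 with. Power goes from 0.7845 to 0.7842.

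**The case against.** The strongest reply is that this is not a defect. A prespecified two-term analysis of covariance is valid and errs on the safe side. At the planned 15 points the power gain is 0.15 to 0.25 of a percentage point. Extra sites are possible, not certain, and no site effect is documented. All of this stands, and it sets the weight of the point: a worthwhile efficiency change, not a repair to validity.

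Three technical objections are also fair:
- **A 5% floor for the site share is arbitrary.** At 2% the gain is 0.6 of a point at 10 points and under 0.1 at 15, as the table shows.
- **18.68 is not the residual SD of the primary model.** The PCL-5 description gives it as the SD of total scores in a first-responder sample, and the sample size section carries it over as the SD of change. The baseline-adjusted residual SD is unknown. The percentage overstatement and the actual type I error do not depend on it; the standard errors, interval widths, powers and sample equivalents do.
- **The normal approximation gives power levels one to two points high at 10 points,** compared with the t-test simulations. The gains are similar under both methods.

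The plan does examine site, so a material effect would be seen. But that separate analysis cannot change the primary standard error or p-value. On imputation, the covariate list is open, so site is not excluded; it is simply not assured, and no size can be put on that part.

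**Conclusion.** The point holds. If Stage 2 enrols at more than one site and site explains part of PCL-5 change after baseline adjustment, the primary test is mildly conservative. For an assumed site share of 5% to 10%, the standard error is overstated by 2.6% to 5.4% and type I error is about 0.043 to 0.038 instead of 0.049. Power forgone is 1.4 to 2.8 percentage points at a 10-point difference and negligible at 15. At an assumed share of 20% the actual type I error would fall to about 0.028, so *mildly* applies up to roughly 10%.

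The treatment estimate is not biased, the false-positive rate is not raised, and the planned sample size is not threatened. With a single site, or no site effect, the gain is zero.

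**What to change.** In Primary outcome efficacy analysis, state that if more than one site enrols in Stage 2:
- site enters the primary regression as a fixed effect, in every imputed data set;
- site is kept in the imputation model and not left to LASSO selection;
- very small sites are pooled by a rule fixed before unblinding.

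Keep the site-by-treatment interaction in the separate poolability analysis. Make the change before unblinding, because adding site afterwards would look data-driven.

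The cost is a short addition to the SAP, one model term and at most three degrees of freedom (105 to 102 with 108 completers). Sample size, visits and data collection do not change.

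### LASSO may leave treatment group out of the imputation model; when it does, the primary estimate shrinks toward zero by about the missing fraction

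*Combined protocol and SAP*

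**What the plan says.** All of this is in the combined protocol and SAP, Statistical Analysis Plan for Stage 2, under the primary outcome efficacy analysis.

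- **Analysis model.** Change in PCL-5 from BL to F1 is regressed in the ITT population, "with independent variables being the BL PCL-5 total score and a dummy variable for the two treatment groups".
- **Imputation model, candidates.** The text reads "covariates considered for inclusion in the model will be the BL PCL-5 total score, a dummy variable for treatment group", followed by examples of auxiliaries: number of treatments, military status, gender, age and PTSD severity.
- **Imputation model, selection.** "The linear regression model will be chosen using the LASSO method with cross-validation, implemented in SAS PROC GLMSELECT". What is fixed beforehand is the candidate list: "The set of variables to be considered for inclusion will be determined before the imputation is performed". No sentence says that treatment or baseline is always retained, and no tuning rule or number of folds is given.
- **Use.** After selection, "at least 20 data sets will be created with the missing F1 PCL-5 values imputed", and the analysis model is fitted to each and the results combined.
- **Sensitivity analyses.** These are "1) analysis of non-missing F1 PCL-5 total scores", plus replacement of missing scores by the best and by the worst possible score. None repeats the multiple imputation with treatment and baseline held in.

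**The concern.** An imputation model should contain at least the terms of the analysis model that will be fitted to the completed data. Here the analysis model has two terms, and a data-driven step may remove either of them from the imputation model. LASSO tuned by cross-validation selects for prediction of the F1 score. It gives no protection to the treatment term, which is the one the trial exists to estimate.

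If treatment is removed, a missing active score and a missing sham score with the same covariates are drawn from the same distribution. Those participants then contribute no treatment difference, and the primary ITT estimate is pulled toward zero. At stake are some power and an understated effect in the primary result, depending on a selection step whose tuning the plan leaves open.

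**Working it through.** **Plan's own figures.** The Stage 2 sample size section gives "group mean pre-post PCL-5 scores = 15, with pooled SD_{difference} = 18.68", two-sided alpha 0.05, 54 completers per group, 10% loss and power 0.985.

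- d = 15/18.68 = 0.803; noncentrality = 0.803 × √(54/2) = 4.17 on 106 df.
- Power from the noncentral t is 0.9852 at alpha 0.05 (stated 0.985) and 0.9371 at alpha 0.01 (stated 0.938).
- 108/0.90 = 120 randomised, as stated.

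The figures reproduce. The Study Design section gives 140 randomised instead. The 120 is used here because it goes with the stated power.

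**Size when treatment is absent from the imputation model.** Let a fraction m be missing in each arm, completely at random. Each arm's completed mean is (1 − m) × its own mean + m × a common mean. The common part cancels in the difference:

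estimated effect = (1 − m) × true effect.

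- m = 0.10: 15 × 0.90 = 13.5; 10 × 0.90 = 9.0.
- m = 0.20 (an assumption): 15 × 0.80 = 12.0.

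Simulation agrees. The set-up was N = 120, 20 imputations, Rubin's rules and the final alpha of 0.049, with 400 trials per row. Assumptions not in the documents: BL mean 45 and SD 12, slope of change on BL −0.4, data missing completely at random.

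| True effect | Missing | Treatment omitted: mean, power | Treatment and BL kept: mean, power |
|---|---|---|---|
| 15 | 10% | 13.45, 0.978 | 15.01, 0.988 |
| 15 | 20% | 12.01, 0.925 | 15.09, 0.988 |
| 10 | 10% | 8.71, 0.728 | 9.69, 0.798 |

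**How often LASSO drops treatment.** Same set-up with 10% missing, uninformative auxiliaries and 5-fold cross-validation. There were 500 trials per row at minimum CV error and 300 under a one-standard-error rule.

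| Tuning | True effect | Treatment dropped | Mean estimate, LASSO vs kept | Power, LASSO vs kept |
|---|---|---|---|---|
| Minimum CV | 15 | 0% | 15.18 vs 15.19 | 0.988 vs 0.990 |
| Minimum CV | 10 | 5% | 9.89 vs 9.95 | 0.802 vs 0.802 |
| Minimum CV | 5 | 35% | 5.06 vs 5.15 | 0.292 vs 0.298 |
| One-SE (assumed) | 15 | 16% | 14.92 vs 15.11 | 0.980 vs 0.987 |
| One-SE (assumed) | 10 | 54% | 9.44 vs 9.88 | 0.713 vs 0.783 |
| One-SE (assumed) | 5 | 91% | 4.33 vs 4.70 | 0.203 vs 0.263 |

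Other simulations with residual SDs of 17 to 18 and five noise covariates put the minimum-CV drop rate at 0.3 to 0.4% for 15 points and 4 to 7% for 10 points. The one-standard-error rate at 10 points was 50 to 55%.

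In the trials where treatment was dropped, the shrinkage was close to the missing fraction. For example, 10.29 against 11.47 is 1 − 10.29/11.47 = 10%, and 1.84 against 2.03 is 9%.

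**Type I error.** At no true effect and minimum CV, rejection was 0.048 with LASSO and 0.054 with both terms kept (500 trials).

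**Baseline alone.** Omitting BL but keeping treatment gave 14.92 against 14.89 (10% missing) and 15.18 against 15.13 (20% missing). There was no attenuation. The power cost was at most about 3 points (0.752 against 0.778 at a true effect of 10).

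**The case against.** The strongest reply is that the loss hardly ever reaches the result. Under minimum-CV tuning LASSO drops treatment mainly when the observed effect is weak, so the trial would usually be non-significant either way. In 300 simulated trials per setting with residual SD 17.5, the LASSO and protected models gave the same significance decision in every trial at 15, 10 and 8 points, and differed in 0.3% at 5 points. This stands. It does not cover sparser tuning: under a one-standard-error rule the same runs changed 0%, 3%, 8.7% and 5.3% of decisions at 15, 10, 8 and 5 points. The plan neither names nor excludes such a rule.

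A second reply is that the bias is conservative and the analysis of observed scores would expose it. Both parts are right, but a sensitivity analysis does not repair the primary estimate.

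Third, the sentence on how the imputed data sets are generated is incomplete in the text as read from the PDF, so silence at that spot is weak evidence. If the full sentence keeps both terms in, the point falls.

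A reader might also infer four stronger things that the documents do not support:

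- **That the primary estimate will be about 10% too small.** That holds only if treatment is dropped, which is rare at the design effect under minimum-CV tuning.
- **That losing baseline also dilutes the effect.** It did not when data were missing completely at random.
- **That a false efficacy claim could follow.** Type I error was not inflated.
- **That clinic must be forced in too.** Clinic is not in the analysis model, so this argument does not reach it.

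**Conclusion.** The gap is real and avoidable, and its expected effect at the planned difference is small. The plan lets a selection step decide whether the imputation model contains the two terms of the primary analysis model. If treatment is dropped, the estimate shrinks by about the missing fraction, 10% at the planned loss.

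With minimum-CV tuning this happens in 0 to 0.4% of simulated trials at 15 points and about 4 to 7% at 10 points, the threshold that the PCL-5 description gives for meaningful change. Mean shrinkage is then under 0.1 points. Smaller true effects and heavier missingness make it matter more. So does a sparser rule: at 10 points the one-standard-error choice cost 7 points of power in one set of runs (0.783 to 0.713) and changed 3% of decisions in another.

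These figures rest on assumed baseline values, uninformative auxiliaries, five folds and data missing completely at random. The proportional shrinkage needs only equal missing fractions, at random, in the two arms. The direction is against the active treatment throughout.

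**What to change.** Add one sentence to the missing-data paragraph before unblinding: treatment group and BL PCL-5 are always in the regression used to impute F1 PCL-5, and LASSO selects only among the auxiliary variables. If the LASSO step cannot hold terms in, add both to the imputation regression after selection. Baseline belongs there because it is in the analysis model and omitting it costs a little power.

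This is a free improvement: one sentence and a small programming change, with no effect on data collection, sample size or conduct. In the simulations at 10% missing, the protected model returned mean estimates of about 15 and 10 at those true effects, with power about 0.99 and 0.80. Recording the tuning rule and number of folds would be good practice, but once both terms are protected those choices affect only the auxiliaries.
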